9.9 Removal of Subjects

Subjects may withdraw from the study at any time at their own request. Subjects may be withdrawn from study drug treatment at any time at the discretion of the investigator or Vertex

Vertex Pharmaceuticals Incorporated

for safety, behavior, noncompliance with study procedures, or administrative reasons. A subject who withdraws from study drug treatment will continue to be followed unless the subject withdraws consent.

Subjects who complete or discontinue study treatment before Day 14 should continue to return for study assessments, as noted in Section 9.1.5.

If a subject does not return for a scheduled visit, reasonable effort will be made to contact the subject. In any circumstance, reasonable effort will be made to document subject outcome. The investigator will inquire about the reason for withdrawal, request that the subject return all unused investigational product(s), request that the subject return for a Safety Follow-up Visit, if applicable (see Section 9.1.5), and follow up with the subject regarding any unresolved AEs.

If a subject withdraws consent for the study, no further assessments will be performed. Vertex may retain and continue using the study data and samples after the study ends and may use the samples and information in the development of the study compound, for other drugs and diagnostics, in publications and presentations, and for education purposes. If a subject withdraws from the study, the study data and samples collected will remain part of the study. A subject will not be able to request the withdrawal of his/her information from the study data. A subject may request destruction of the samples collected from him/her during the study as long as those samples can be identified as his/her samples.

9.10 Replacement of Subjects

Subjects who withdraw or are withdrawn during the study drug Treatment Period will not be replaced.

10 STUDY DRUG INFORMATION AND MANAGEMENT

Study drug refers to VX-548 (Section 10.1 through Section 10.7). Vertex will also supply the commercially available rescue medication (Section 10.8).

10.1 Preparation and Dispensing

Study drug may be dispensed only under the supervision of the investigator or an authorized designee and only for administration to the study subjects.

Tablets will be dispensed at the site to individual dosing containers by a qualified pharmacist or designated study site staff, and following national and local laws and regulations.

10.2 Packaging and Labeling

Vertex will supply the 50-mg VX-548 tablets. Study drug labeling will be in compliance with applicable local and national regulations. Additional details about packaging, labeling, and dispensing for VX-548 will be in the Pharmacy Manual.

10.3 Study Drug Supply, Storage, and Handling

The investigator, or an authorized designee (e.g., a licensed pharmacist), will ensure that all investigational product is stored in a secured area, under recommended storage conditions, and in accordance with applicable regulatory requirements. To ensure adequate records, all study drugs will be accounted for via the drug accountability forms as instructed by Vertex.

Study drug supply details are listed in Table 10-1. Detailed instructions regarding the storage, handling, and dispensation of the study drug will be provided in the Pharmacy Manual.

	Study Drug		
	Dosing Form/		
Drug Name	Route	Dosage	How Supplied
	Tablet/	100 mg first dose; all other	
VX-548	oral	doses 50 mg	Supplied as 50-mg tablets

Table 10-1Study Drug

10.4 Drug Accountability

The pharmacist or designated study site staff will maintain information about the dates and amounts of (1) study drug received; (2) study drug dispensed to the subjects; and (3) study drug returned by the subjects. Subjects will be instructed to return all used and unused materials associated with the study drug to the site. These materials will be retained at the site according to instructions provided by Vertex or its designee. The study monitor will review study drug records and inventory throughout the study. If a site uses a site-specific drug accountability system and/or process, including processes associated with the destruction of returned materials, the process must be documented and approved by Vertex. The study monitor must review the drug accountability documentation on a regular basis. The study monitor will promptly communicate to Vertex any discrepancies he/she is unable to resolve with the site.

10.5 Disposal, Return, or Retention of Unused Drug

The study site staff or pharmacy personnel will retain all materials returned by the subjects until the study monitor has performed drug accountability. The investigator will ensure that the materials are destroyed in compliance with applicable environmental regulations, institutional policy, and any special instructions provided by Vertex. Destruction will be adequately documented.

The principal investigator, study site staff, including pharmacy personnel will assist Vertex with any recall activities (as applicable) and place impacted investigational medicinal product (IMP) in quarantine when requested.

10.6 Compliance

To ensure treatment compliance, the investigator or designee will supervise all study drug dosing that occurs at the site. At each visit, site personnel or approved home nurse will review that the subject is compliant with study drug dosing and remind the subject of study drug dosing requirements. Compliance will also be assessed by ongoing study drug count in the clinic or checked by home nurse during home visits.

If a subject demonstrates continued noncompliance of study drug dosing despite educational efforts, the investigator should consider discontinuing the subject from the study.

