9.1.3 Treatment Period

Treatment Period assessments are listed in Table 3-4 (surgical and non-surgical subjects).

All study periods will be conducted as described in Section 9.1. Dosing details are in Section 9.6.

If a subject has any clinically significant, study-related abnormalities at the time that they meet discharge/leaving criteria from where the surgical procedure was conducted or non-surgical condition was treated (e.g., hospital, clinic, or ambulatory center), the medical monitor (or authorized designee) will be notified, and the subject will be asked to remain (e.g., in the hospital, clinic, or ambulatory center) until such abnormalities resolve. If the subject is unable or unwilling to remain, the medical monitor (or authorized designee) will be notified, and the investigator will make every effort to arrange follow-up evaluations at appropriate intervals to document the course of the abnormalities.

Although the inpatient period, if any, is generally expected to be <24 hours (Section 8.1), subjects who turn out to require a stay of \geq 24 hours do not need to discontinue study drug treatment or the study.

Subjects who complete or discontinue study drug treatment before Day 14 will remain in the study from the time of stopping study drug treatment through the last scheduled study visit and complete assessments for all study visits, as described in Section 9.1.5.

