9.2.5 Study Drug Exposure and Study Drug Compliance

Study drug exposure (in days) will be calculated as (last date of dosing – first date of dosing) + 1. This will be summarized overall, as well as for those who completed treatment and for those who discontinued treatment. Study drug exposure will also be summarized in categories: ≤ 3 days, >3 to ≤ 7 days, and >7 days, using counts and percentages.

Compliance will not be analyzed due to the complex nature of starting and stopping the study drug as explained in Section 9.1 of the CSP.

All data collected during dispensation of study drug (e.g., time of administration and number of tablets taken) will be presented in an individual data listing.

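### Protocol 10.6 has investigators consider taking dosing-noncompliant subjects out of the study, while 9.9, 9.1.3 and 9.1.5 keep subjects who stop drug in follow-up; safety data could be truncated, probably with small effect

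*Protocol*

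**What the plan says.** Protocol 10.6 (Compliance) sets the trigger, "If a subject demonstrates continued noncompliance of study drug dosing despite educational efforts", and the response: "the investigator should consider discontinuing the subject from the study". It gives no numeric threshold.

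Protocol 9.9 (Removal of Subjects) covers the same ground differently. "Subjects may be withdrawn from study drug treatment at any time at the discretion of the investigator or Vertex", and the reasons listed are "for safety, behavior, noncompliance with study procedures, or administrative reasons". It adds that a subject "who withdraws from study drug treatment will continue to be followed unless the subject withdraws consent". In that section, leaving the study is at the subject's own request; the authority given to the investigator and sponsor concerns study drug.

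Protocol 9.1.3 (Treatment Period) says that subjects who complete or discontinue drug before Day 14 "will remain in the study from the time of stopping study drug treatment through the last scheduled study visit". Section 9.1.5 calls for an End of Dosing Visit when drug stops early for any reason, and makes the Safety Follow-up Visit a requirement for these subjects.

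On analysis, SAP 9.2.5 states: "Compliance will not be analyzed due to the complex nature of starting and stopping the study drug". Dosing data are listed by subject, and SAP 9.2.1 tabulates premature discontinuation of treatment and of study, each with reasons.

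**The concern.** Two sites could handle the same noncompliant subject in opposite ways, and each could cite the protocol. One would stop drug and keep the subject through Day 28; the other would end participation.

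The difference matters because safety is the primary objective and there is one arm. Under Protocol 9.1.7, a subject with no Safety Follow-up Visit completes participation at last contact. The treatment-emergent period, as defined in Protocol 12.3.1 and SAP 9.1, closes there too. The subject has been dosed, so remains in the Safety Set, and under 9.10 is not replaced. The result would be a shortened observation window in an unchanged denominator, concentrated in noncompliant subjects. If noncompliance happened to go with poor tolerability, the truncation would be informative.

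**Working it through.** **1. Is the wording in 10.6 only a loose synonym for stopping drug?** The documents suggest not. Section 9.1.3 names discontinuing study drug treatment and discontinuing the study as separate things when it discusses stays of 24 hours or more. SAP 9.2.1 counts them in separate disposition categories. A literal reader of 10.6 would take it to mean the study.

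**2. What a literal removal would cost one subject.** The planned window is 28 days.
- Last contact on Day 7: 28 − 7 = 21 days lost; 21/28 = 75%.
- Last contact on Day 14: 28 − 14 = 14 days lost; 14/28 = 50%.

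Any scheduled laboratory tests, ECGs and C-SSRS not yet done would also be missed.

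**3. The plan's own figure.** Protocol 12.1 and SAP 7.1 give 92% and 99% as the probability of seeing an event in at least one of 250 subjects at true incidence 1% and 2%. With P = 1 − (1 − p)^n:
- p = 1%: 1 − 0.99^250 = 91.9%.
- p = 2%: 1 − 0.98^250 = 99.4%.

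Both agree with the stated figures.

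**4. Effect of lost follow-up on that figure.** The documents give no removal rate, so the fractions below are assumptions. The worst case treats removed subjects as giving no safety data at all, so n falls (at 5%, 250 × 0.95 = 237.5, taken as 238). The milder case lets them keep half their window under a constant hazard, so each counts as half a subject.

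| Assumed share removed | n, worst case | P at 1%, worst case | P at 2%, worst case | P at 1%, half window kept |
|---|---|---|---|---|
| 0% | 250 | 91.9% | 99.4% | – |
| 2% | 245 | 91.5% | 99.3% | 91.7% |
| 5% | 238 | 90.9% | 99.2% | 91.4% |
| 10% | 225 | 89.6% | 98.9% | 90.8% |
| 20% | 200 | 86.6% | 98.2% | 89.6% |

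**5. Effect on observed incidence.** Suppose a share d is removed with no data, and that their event rate is RR times the rate p in the others. True incidence is (1 − d)p + d·p·RR; observed incidence is (1 − d)p. With p = 2%:
- d = 5%, RR = 1: true 2.0%, observed 1.9%.
- d = 5%, RR = 3: true 2.2%, observed 1.9%.
- d = 10%, RR = 3: true 2.4%, observed 1.8%.

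If 5% instead lose 75% of their window under a constant hazard with RR = 1, an incidence of 1% becomes about 1% × (1 − 0.05 × 0.75) = 0.96%. In every case the observed figure is equal to or below the true one. The gap is small unless removals are common and noncompliers differ markedly.

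**The case against.** The strongest reply is that other sections largely prevent the loss. Section 10.6 is discretionary and applies only after education has failed. A subject removed before Day 14 also stops drug, and 9.1.5 then calls for the End of Dosing Visit and requires the Safety Follow-up Visit. Sections 9.1.5 and 9.9 rule out further assessments only on withdrawal of consent. Section 9.9 also asks for reasonable effort to document outcome, for a request that the subject attend a Safety Follow-up Visit where applicable, and for follow-up of unresolved adverse events. Section 13.1.1.7 follows each event until the investigator gives a final outcome. SAP 9.2.1 would make removals visible.

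Much of this stands, and it is why truncation is a possibility and not an established loss. It does not remove the conflict. The request in 9.9 sits in the paragraph on missed visits and is weaker than the requirement in 9.1.5. Following known events does not capture new ones. A disposition table shows that data are missing without recovering them.

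Three stronger readings are tempting, and the documents do not support them.
- A reader might infer that sites have no usable measure of compliance, since the SAP does not analyse it. But 10.6 provides review at each visit and drug counts, doses are timed in an e-diary, and 9.6 defines dosing windows and missed-dose handling. What is absent is a threshold.
- A reader might infer that the end-of-treatment PGA would fall back to an earlier rating. But Table 3-4 has subjects who stop drug complete it at home within about 24 hours of the last dose, and SAP Appendix A accepts the first rating within 48 hours.
- A reader might set an assumed 2–5% removed (5 to 13 subjects) against the 1–2% event rates used for sample size. These are different quantities: at 1% incidence, 13 subjects contribute 13 × 0.01 = 0.13 expected events in all.

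**Conclusion.** The inconsistency between 10.6 and 9.9, 9.1.3 and 9.1.5 is real and worth correcting, because it touches data for the primary endpoint. Followed literally, 10.6 can truncate safety follow-up in noncompliant subjects who stay in the denominator, and the direction of any effect on treatment-emergent event incidence is nil or downward.

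The likely size is small. At an assumed 5% with no data at all, detection of a 1% event loses about one percentage point (91.9% to 90.9%); at an assumed 20% it loses about five (91.9% to 86.6%).

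A reader might go further and conclude that safety follow-up will be lost, or that the safety results will be biased low. Neither follows: removal is only to be considered, no rate is given, other sections partly mitigate, and nothing in the documents ties noncompliance to tolerability.

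**What to change.** Reconcile Protocol 10.6 with 9.9, 9.1.3 and 9.1.5 so that all four say the same thing about whether dosing noncompliance ends study drug or study participation. State alongside it that the End of Dosing and Safety Follow-up assessments already set out in 9.1.5 are still collected unless the subject withdraws consent. Whether and when to stop drug remains for the sponsor and investigator to decide.

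The cost is about one phrase in 10.6. The visits are already scheduled for subjects who stop drug early, so no new assessment is needed, and the SAP needs no change.

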10.7 Blinding and Unblinding

This is an open-label study.

10.8 Rescue Medication

Vertex will supply acetaminophen and ibuprofen for use as rescue medication during the Treatment Period. Drug accountability will be performed in a similar manner as for study drug.

11 ASSESSMENTS

The schedule of assessments is shown in Table 3-1, Table 3-2, Table 3-3, and Table 3-4.

11.1 Subject and Disease Characteristics

Subject and disease characteristics include the following: demographics, medical and surgical history, baseline VRS and NPRS scores, type of surgical procedure (for surgical subjects only), height, and weight.

Medical history will be elicited from each subject and extracted from medical records during screening. Based on the medical history, the subject will be assessed for any disqualifying medical conditions as specified in the inclusion and exclusion criteria (Section 8). The medical history will include a complete review of systems, past medical and surgical histories, concomitant medications, and any allergies.

11.2 Pharmacokinetics

Not applicable

11.3 Other Assessments

11.3.1 Use of Rescue Medications

Rescue medication is permitted for pain relief if needed. Guidelines on administration of ibuprofen and acetaminophen in combination as rescue medications are included in Section 9.4.1.2. Subjects will record rescue medication use in an e-diary; a paper back-up option will be available.

11.4 Effectiveness

11.4.1 Patient Global Assessment of Study Drug

The PGA of study drug is completed after taking a dose of study drug, at the indicated time points. Subjects should still complete the PGA even if the specified dose is not taken (e.g., forgotten dose). Detailed procedures for the administration of the PGA of study drug will be provided in a separate document. Subjects will record their PGA responses in an e-diary; a paper back-up option will be available.

11.5 Safety

Safety evaluations will include AEs; clinical laboratory assessments; clinical evaluation of vital signs, standard 12-lead ECGs, and physical examinations (PEs); and Columbia-Suicide Severity Rating Scale (C-SSRS).

11.5.1 Adverse Events

All AEs will be assessed, documented, and reported in accordance with current ICH E6 GCP Guidelines. Section 13.1 outlines the definitions, collection periods, criteria, and procedures for documenting, grading, and reporting AEs.

11.5.2 Clinical Laboratory Assessments

Blood and urine samples will be analyzed at a central laboratory, unless otherwise specified.

Laboratory test results that are abnormal and considered clinically significant will be reported as AEs (see Section 11.5.1).

The safety laboratory test panels are shown in Table 11-1.

Serum Chemistry	Hematology	Urinalysis ^a
Glucose	Hemoglobin	Urobilinogen
Blood urea nitrogen ^b	Platelets	Urine protein
Creatinine	Leukocytes	pH
Sodium	Differential (percent):	Urine blood
Potassium	Eosinophils	Specific gravity
Calcium	Basophils	Urine ketones
Chloride	Neutrophils	Urine bilirubin
Magnesium	Lymphocytes	Urine glucose
Bicarbonate	Monocytes	
Phosphate	Coagulation	
Total bilirubin, direct bilirubin	Activated partial thromboplastin time	
Alkaline phosphatase	Prothrombin time	
Aspartate transaminase	Prothrombin time International	
Alanine transaminase	Normalized Ratio	
Amylase		
Lipase		
Gamma-glutamyl transferase		
Protein		
Albumin		
Creatine kinase		
Urate		

Table 11-1Safety Laboratory Test Panels

^a If urinalysis results are positive for protein or blood, microscopic examination of urine will be done, and results will be provided for leukocytes, erythrocytes, crystals, bacteria, and casts.

^b If blood urea nitrogen cannot be collected, urea may be substituted.

Clinical laboratory assessments during screening must have no clinically significant findings that preclude participation in the study, as judged by the investigator, for a subject to receive study drug on Day 1. For non-surgical subjects, local laboratory results will be used during screening; previous test results from the facility's local laboratory may be used to establish eligibility if collected within 2 hours before ICF signing.

Additional Screening Tests: The following additional tests will be performed at the Screening Visit and/or pre-procedure to assess eligibility:

- Serology (surgical subjects only): Hepatitis B surface antigen (HBsAg), hepatitis C virus antibody (HCV Ab), HCV RNA, and antibodies against human immunodeficiency viruses 1 and 2 (HIV-1/HIV-2 Abs). Subjects with detectable viral load will be excluded (Section 8.2).
- Serum Follicle-stimulating Hormone (FSH): Serum FSH will be tested at the Screening Visit for female subjects who are suspected to be postmenopausal (as defined in Section 11.5.6.1). For a subject to be considered of non-childbearing potential, the serum FSH levels will be

within the laboratory range for postmenopausal females. For non-surgical subjects, a test result is not required for eligibility; however, until the test result is received, a subject will be considered to be of childbearing potential and must follow contraception requirements (Section 11.5.6.1) until postmenopausal status is confirmed.

- Pregnancy Testing: Surgical subjects: All biologically female subjects will have a serum beta-human chorionic gonadotropin (β-hCG) test during the Screening Visit. Female subjects of childbearing potential (Section 11.5.6.1) will also have a urine β-hCG test before admission on Day 1. Both the serum and urine β-hCG test must be negative to receive study drug. Non-surgical subjects: All biologically female subjects will have a urine β-hCG test during the Screening Visit, which occurs on Day 1; the test must be negative to receive study drug.
- Drug and Alcohol Screening: Drug screening for opioids, methadone, cannabinoids, cocaine, amphetamines/methamphetamines, barbiturates, and benzodiazepines will be assessed by a urine test at the Screening Visit and before admission on Day 1; for non-surgical subjects, only 1 test is required because the Screening Visit is on Day 1. Alcohol screening will be assessed before admission (surgical subjects) or treatment assignment (non-surgical subjects) on Day 1 by a urine, blood, or breath test. Subjects may undergo random urine drug screen and alcohol testing if deemed appropriate by the investigator. Drug and alcohol screen results must be negative for a subject to receive study drug; a positive marijuana screen will only be exclusionary on Day 1. A positive drug screen for a known prescribed concomitant medication that is not otherwise exclusionary (e.g., benzodiazepines) will not disqualify subjects.

Additional Evaluations: Additional clinical laboratory evaluations will be performed at other times if judged to be clinically appropriate.

For purposes of study conduct, only laboratory tests done in the central laboratory may be used, with the following exceptions:

- Day 1 (pre-procedure, if applicable) drug and alcohol tests and urine β -hCG pregnancy tests will be assessed by staff onsite.
- For **non-surgical subjects**, local laboratories will be used for safety laboratory tests at screening.
- For **surgical subjects**, local laboratories may be used to repeat a screening assessment to determine eligibility on Day 1 (pre-procedure) if there is clear evidence of laboratory error (Section 9.1.1.1) in the central laboratory assessment.

Local laboratories may be used at the discretion of the local investigator for management of urgent medical issues. If a local laboratory test value is found to be abnormal and clinically significant, it will be verified by the central laboratory as soon as possible after the investigator becomes aware of the abnormal result. If it is not possible to send a timely specimen to the central laboratory (e.g., the subject was hospitalized elsewhere), the investigator may base the assessment of an AE on the local laboratory value.

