12 STATISTICAL ANALYSIS

12.1 Sample Size and Power

Approximately 250 subjects are planned to be enrolled. With 250 subjects, there is a 92% probability of observing an AE in at least 1 subject if the true incidence is 1% and a 99% probability of observing an AE in at least 1 subject if the true incidence is 2%.

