9 STATISTICAL ANALYSIS

9.1 General Considerations

The Schedule of Assessments is provided in Section 3 of the CSP. The precision standards for reporting variables are provided in an internal Biometrics document that specifies the programming rules including the precision for derived variables.

All individual subject data for subjects who have received at least 1 dose of study drug will be presented in individual subject data listings.

Continuous variables will be summarized using the following descriptive summary statistics: the number of subjects (n), mean, standard deviation (SD), median, minimum value (min), and maximum value (max).

Categorical variables will be summarized using counts and percentages.

Baseline value, unless specified otherwise, will be defined as the most recent non-missing measurement (scheduled or unscheduled) collected before the first dose of study drug.

For ECGs, the baseline value will be defined as the average of the most recent non-missing measurements (scheduled or unscheduled) collected before the first dose of study drug, expected to be the triplicate predose measurements on Day 1.

Change (absolute change) from baseline will be calculated as post-baseline value – baseline value.

Treatment-emergent (TE) Period will include the time from the first dose of study drug to the Safety Follow-up Visit or to the completion of study participation (as defined in Section 9.1.7 of the CSP), whichever occurs first.

Unscheduled visits: Unscheduled visit measurements will be included in the analysis as follows:

• In scheduled visit windows per specified visit windowing rules

- In the derivation of baseline
- In the derivation of maximum and minimum values during the TE period, and maximum and minimum change from baseline values during the TE period for safety analyses
- In individual subject data listings as appropriate

Visit windowing rules: The analysis visit windows for protocol-defined PGA entries, which are provided by the subject in a dosing diary, are provided in Appendix A. All safety assessments are analyzed according to their nominal visits.

Outliers: No formal statistical analyses will be performed to detect and/or remedy the presence of statistical outliers.

Multiplicity: Only descriptive analyses will be performed; no statistical hypothesis testing will be performed.

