9.4.2 Clinical Laboratory Assessments

All statistical analyses of laboratory values will be performed using SI units. For treatmentemergent laboratory measurements, the observed values and change from baseline values of the continuous hematology, chemistry, and coagulation results will be summarized at each visit.

The number and percentage of subjects with selected test values meeting threshold analysis criteria during the TE period will be summarized. The number and percentage of subjects with shift from baseline in selected test values meeting threshold analysis criteria will also be summarized for chemistry measurements. The threshold analysis criteria are provided in Appendix D.

Results of urinalysis and the urine/serum pregnancy test will be in individual subject data listings only.

In addition, listings of individual subject hematology, chemistry, and coagulation values outside the normal reference ranges will be provided. These listings will include data from both scheduled and unscheduled visits.

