Appendix D: Threshold Value Criteria

Parameter	Threshold Analysis	Comments
Clinical Chemistry		
ALT	>ULN - ≤3xULN >3x - ≤5xULN >5x - ≤8xULN >8x - ≤20xULN >20xULN	FDA DILI Guidance Jul 2009.
AST	>ULN - ≤3xULN >3x - ≤5xULN >5x - ≤8xULN >8x - ≤20xULN >20xULN	FDA DILI Guidance Jul 2009.
ALT or AST	$\begin{array}{l} (ALT>ULN - \leq 3xULN) \text{ or } (AST>ULN - \\ \leq 3xULN) \\ (ALT>3x - \leq 5xULN) \text{ or } (AST>3x - \\ \leq 5xULN) \\ (ALT>5x - \leq 8xULN) \text{ or } (AST>5x - \\ \leq 8xULN) \\ (ALT>8x - \leq 20xULN) \text{ or } (AST>8x - \\ \leq 20xULN) \\ ALT>20xULN \text{ or } AST>20xULN \end{array}$	- FDA DILI Guidance Jul 2009.
Alkaline Phosphatase	>ULN - ≤1.5xULN >1.5 - ≤2.5xULN >2.5 - ≤5xULN >5 - ≤20xULN >20xULN	FDA DILI Guidance Jul 2009.
Total Bilirubin	>ULN - ≤1.5xULN >1.5 - ≤2xULN >2 - ≤3xULN >3 - ≤10xULN >10xULN	FDA DILI Guidance Jul 2009.
Direct Bilirubin	>ULN - ≤1.5xULN >1.5 - ≤2xULN >2 - ≤3xULN >3 - ≤10xULN >10xULN	FDA DILI Guidance Jul 2009.
ALT and Total Bilirubin	ALT>3xULN and TBILI>2xULN	FDA DILI Guidance Jul 2009.
AST and Total Bilirubin	AST>3xULN and TBILI>2xULN	FDA DILI Guidance Jul 2009.
(ALT or AST) and Total Bilirubin	(ALT>3xULN or AST>3xULN) and TBILI>2×ULN	FDA DILI Guidance Jul 2009.

Parameter	Threshold Analysis	Comments
GGT	>ULN - ≤2.5xULN >2.5 - ≤5xULN >5 - ≤20xULN >20xULN	CTCAE grade 1-4
Albumin	<lln -="" g="" l
<30 - ≥20 g/L <20 g/L</lln>	CTCAE grade 1-3
Creatinine	>ULN - ≤1.5xULN >1.5 - ≤3xULN >3 - ≤6xULN >6xULN	CTCAE grades 1-4
Lipase	>ULN - ≤1.5xULN >1.5x - ≤2xULN >2x - ≤5xULN >5xULN	Criteria based upon CTCAE
Total protein	<lln >ULN</lln 	No CTCAE
Creatine kinase	>ULN - ≤2.5xULN >2.5 - ≤5xULN >5 - ≤10xULN >10xULN	CTCAE grades 1-4
Hematology		
Hemoglobin	Hgb decreased (anemia) <lln -="" g="" l
<100 - ≥80 g/L <80 g/L</lln>	CTCAE grade 1-3
	Hgb increased >ULN - ≤20 g/L above ULN >20 g/L above ULN - ≤40 g/L above ULN >40 g/L above ULN	CTCAE grade 1-3
Platelets	Platelet decreased <lln -="" 10e9="" l
<75.0 - ≥50.0 x 10e9 /L <50.0 - ≥25.0 x 10e9 /L <25.0 x 10e9 /L</lln>	CTCAE grade 1-4
	Platelet increased >ULN	No CTCAE available
Coagulation		
Activated partial thromboplastin time (PTT)	>ULN - ≤1.5xULN >1.5 - ≤2.5xULN >2.5xULN	CTCAE grade 1-3

Table 12-3 Threshold Analysis Criteria for Laboratory Tests (as applicable)

Parameter	Threshold Analysis	Comments
Prothrombin time (PT)	>ULN - ≤1.5xULN	CTCAE grade 1-3
International	>1.5 - ≤2.5xULN	
Normalized Ratio (INR)	>2.5 x ULN	

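### No planned laboratory table gives absolute neutrophil or lymphocyte counts, or the number of subjects with low leukocytes or neutrophils

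*Protocol*

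**What the plan says.** - **Collection.** In Protocol 11.5.2, Table 11-1, leukocytes are a separate hematology test. Eosinophils, basophils, neutrophils, lymphocytes and monocytes stand under the label "Differential (percent".
- **By-visit summary.** SAP 9.4.2 states that "the observed values and change from baseline values of the continuous hematology, chemistry, and coagulation results will be summarized at each visit". SAP 9.1 sets the statistics: "the number of subjects (n), mean, standard deviation (SD), median, minimum value (min), and maximum value (max". Neither document says that absolute differential counts will be derived.
- **Threshold counts.** SAP 9.4.2 also says: "The number and percentage of subjects with selected test values meeting threshold analysis criteria during the TE period will be summarized". In Appendix D, Table 12-3, the hematology block holds hemoglobin ("Hgb decreased (anemia", then increased) and platelets ("Platelet decreased", then increased). Coagulation follows. Shift-from-baseline summaries are limited to chemistry.
- **Other routes.** SAP 9.4.2 lists individual hematology values outside the reference range, from scheduled and unscheduled visits. Protocol 11.5.2 turns clinically significant abnormal results into adverse events, and SAP 9.4.1 tabulates the treatment-emergent ones.
- **Timing.** For surgical subjects, the only scheduled hematology sample before dosing is at Screening, Day -28 to Day -1 (Table 3-1). The next is postdose, at discharge (Table 3-4).

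**The concern.** A differential percentage is a share of the total. If all white cells fall together, no share changes. If one line rises or falls alone, the shares of the others move although their counts do not. Summaries of change in percent can therefore miss a real fall in neutrophils, or suggest a change in lymphocytes or eosinophils that did not occur.

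The total leukocyte count partly covers this, but the summary gives only its distribution at each visit. Threshold tables exist to say how many subjects went below a limit, whatever the investigator made of the result. The SAP does this for hemoglobin and platelets and not for white cells. Laboratory results are part of the primary endpoint, so the omission is worth closing.

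**Working it through.** **1. The plan's own figure.** Protocol 12.1 gives a "92% probability of observing an AE in at least 1 subject if the true incidence is 1" percent, and 99% at 2%. The formula is 1 - (1 - p)^250:
- p = 0.01: 1 - 0.99^250 = 0.919
- p = 0.02: 1 - 0.98^250 = 0.994

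Both figures reproduce. They concern adverse events, and nothing below changes them.

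**2. What each planned output carries.**

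| Output | Total leukocytes | Absolute neutrophils, lymphocytes | Number of subjects with low values |
|---|---|---|---|
| By-visit summary (SAP 9.4.2) | yes, with min and max | no, percent as collected | no |
| Threshold table (Table 12-3) | no row | no row | no |
| Shift table (SAP 9.4.2) | no, chemistry only | no | no |
| Out-of-range listing | yes | no | no, single results |
| TEAE tables (SAP 9.4.1) | as an event term | as an event term | only if clinically significant |

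Protocol 13.1.1.2 ties clinical significance to related signs or symptoms, further testing or intervention, or a dose change or discontinuation, and leaves the decision to the investigator. A silent fall need not qualify, and then no row of this table counts it.

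**3. How percentages behave.** The documents give no white-cell values, so all of these are assumed (x10^9/L). Absolute count = leukocytes x percent / 100.

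| Case | Leukocytes | Neutrophils | Neutrophil % | Lymphocytes | Lymphocyte % |
|---|---|---|---|---|---|
| Baseline | 6.0 | 3.6 | 60 | 1.8 | 30 |
| (a) all lines fall 75% | 1.5 | 0.9 | 60 | 0.45 | 30 |
| (b) neutrophils alone fall | 3.3 | 0.9 | 27.3 | 1.8 | 54.5 |
| (c) neutrophils alone rise | 9.6 | 7.2 | 75 | 1.8 | 18.8 |

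In (a) every percentage change is zero while neutrophils fall from 3.6 to 0.9. In (b) and (c) the lymphocyte percentage moves by +24.5 and -11.2 points with the count fixed at 1.8. In (a) and (b) total leukocytes do fall, by 4.5 and 2.7. The product returns the right count each time, for example 3.3 x 27.3 / 100 = 0.9.

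**4. What the leukocyte summary shows.** Assume that k of 250 subjects have a fall d, that the others do not change, and that all have a sample at the visit. The mean then changes by k x d / 250.

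| k of 250 | d = -2.7 (case b) | d = -4.5 (case a) |
|---|---|---|
| 1 (0.4%) | -0.011 | -0.018 |
| 3 (1.2%) | -0.032 | -0.054 |
| 5 (2.0%) | -0.054 | -0.090 |
| 13 (5.2%) | -0.140 | -0.234 |

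The mean barely moves. The minimum does show that at least one subject fell to 3.3 or 1.5, but it is the same for one subject as for thirteen and gives no neutrophil value.

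**5. Timing.** On the scheduled samples, a surgical subject's change at discharge spans the operation. If neutrophils rise after surgery (an assumption), that change resembles case (c). The SAP baseline also accepts an unscheduled sample before the first dose, so a subject who has one after surgery would be an exception.

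**The case against.** The strongest reply is that existing provisions cover most of this. Total leukocytes are tabulated at each visit with minimum and maximum, and in the cases where percentages hide or distort a fall the leukocyte count falls too. SAP 9.1 brings unscheduled values into the treatment-emergent minimum. Out-of-range results are listed, and a clinically significant leukopenia or neutropenia gets an incidence in the TEAE tables. The threshold list is declared to be a selection. Neither document names a white-cell signal for VX-548, dosing lasts at most 14 days, and the study is descriptive. Programming rules sit in an internal document, which might already derive absolute counts.

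Most of that stands, and it defeats three stronger readings.
- A reader might infer that a fall in neutrophils leaves no count in any safety table, or would be invisible. It would not: the leukocyte summary and its minimum, the listing and the adverse-event route all remain.
- A reader might infer that the tables fail the purpose for which the trial was sized. The 1% and 2% figures concern adverse events, which the plan does count by subject.
- A reader might infer that absolute counts would separate drug from surgery. They would not in a single-arm study, since a postoperative rise moves absolute neutrophils too. They show which cell line moved, and no more.

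What the reply does not supply is the number of subjects with low leukocytes or neutrophils that the investigator did not report, or any absolute neutrophil or lymphocyte value in a table. An unseen internal document cannot be relied on for that.

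**Conclusion.** The point holds as a reporting gap of small size. As the documents stand, no laboratory table reports absolute neutrophil or lymphocyte counts or counts subjects with low leukocytes or neutrophils. Falls not considered clinically significant therefore have no incidence, and differential percentages can shift without a change in the cell line named. This rests on reading Table 11-1, SAP 9.4.2 and Table 12-3 together. The numerical cases only illustrate the mechanism, with assumed values.

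Nothing is lost irrecoverably, because leukocytes and percentages are both collected. The sample size and its justification are unaffected. I would label this a cheap improvement.

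**What to change.** - **SAP 9.4.2:** derive the absolute count of each cell type as leukocytes x percent / 100 at every time point where both are available. Summarise observed values and changes from baseline on those counts, and keep the percentages in listings.
- **SAP Table 12-3:** add decreased leukocytes and decreased absolute neutrophils, graded by the CTCAE version cited in Protocol 13.1.1.4 (Version 5.0). Rows for lymphocytes and eosinophils are optional.

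The cost is one set of derived variables and a few more table rows. No new sample, visit or change in study conduct is needed.
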